## 2) Objectives

The overall objective of this study is to test the efficacy of virtual family-centered rounds (FCR) compared to standard rounds for NICU patients and to conduct an intervention evaluation of the virtual FCR intervention.

**Aim 1: Evaluate the impact of virtual FCR on parental activation and wellbeing.** The primary outcome will be FCR parent attendance proportion (number of round encounters with a parent present – either virtually or in person – divided by total number of round encounters). Increased parent FCR attendance would increase the delivery of best practice. We will also compare parent experience (Child HCAHPS) and parent activation (P-PAM) at discharge and parent distress and quality of life at 0, 30, 60, and 90 days from discharge between assigned trial arms. Parent wellbeing promotes neonatal wellbeing.

- *Hypothesis1a: The virtual FCR (intervention) group will have a higher parent FCR attendance proportion compared to the standard FCR (control) group.*
- *Hypotheses1b: Parents of virtual FCR neonates will report (a) better experience, (b) higher activation, (c) less distress, and (d) better quality of life compared to parents of standard-of-care neonates.*

**Aim 2: Evaluate the impact of virtual FCR on neonatal outcomes.** We will compare breast milk feeding at discharge and 90 days from discharge, growth failure, medical errors, and NICU length of stay between assigned trial arms.

- *Hypotheses2: Virtual FCR neonates will have (a) greater breast milk feeding, (b) reduced growth failure, (c) fewer errors, and (d) shortened length of stay compared to standard-of-care neonates.*

**Aim 3: Conduct a mixed methods evaluation of the virtual FCR intervention.** We will measure all five RE-AIM dimensions using quantitative (chart review, surveys) and qualitative (observations, interviews) methods. Observations will be of NICU FCR; interviews will be with intervention arm parents and NICU providers. We will use a convergent design and merge data in the analysis and reporting phases.

## 3) Background

Family-centered rounds (**FCR**) are multidisciplinary bedside rounds for hospitalized patients with active engagement by the family. FCR provides many benefits to patients, families, and providers, including fewer harmful errors, shortened hospital stays, reduced parental anxiety, improved family experience, and enhanced staff teamwork. For these reasons, FCR is recognized as a best practice for hospitalized children. However, because active family engagement is required, FCR has only been possible for patients whose families can physically be at the bedside during hospital rounds.

In the neonatal intensive care unit (**NICU**), barriers exist that limit family presence at the bedside. Critically ill neonates may be hospitalized for extended

**PROTOCOL TITLE: Virtual Family-Centered Rounds in the Neonatal Intensive Care Unit:  
A Randomized Clinical Trial**

periods of time. Their parents or guardians (“parents” hereafter) often live far from the hospital and have travel, financial, work, or childcare constraints that limit their ability to be physically present in the NICU. These barriers are particularly challenging for rural and low-income parents. NICU parents have high rates of depression, anxiety, and post-traumatic stress, and reduced visitation with their infant can exacerbate their depression and inhibit parental-newborn attachment. These parental factors impact the neonate, too. Early attachment impacts intelligence and emotional wellbeing later in life. Parental psychological support and engagement can shorten the NICU hospitalization and facilitate breast milk feeding. Breast milk fed infants have improved near-term (e.g., lower risk of sepsis and improved cognitive development) and long-term outcomes (e.g., lower risk of hypertension, diabetes, and obesity).

Telehealth is a potential solution to mitigate these challenges. Using existing secure technology, parents can be virtually present at their neonate’s bedside to participate in FCR. Prior pediatric and adult research suggests that virtual FCR is feasible and meaningful to patients, families, and clinicians. However, these studies had many limitations in sample size, randomization, and outcomes measured. Therefore, we propose a rigorous virtual FCR efficacy trial to understand the impact of telehealth on neonatal and parental outcomes.

#### **4) Inclusion and Exclusion Criteria**

This study is a randomized trial to compare virtual family-centered rounds (**FCR**) to standard FCR for neonatal intensive care unit (**NICU**) patients. We will simultaneously conduct an intervention evaluation of this virtual FCR intervention. The unit of randomization is at the subject level (the neonate). The site is the UC Davis NICU. To gather necessary data on efficacy outcomes and on the 5 dimensions for the intervention evaluation (Reach, Effectiveness, Adoption, Implementation, Maintenance), survey data will be collected from the subjects’ parent or guardian (referred to as “parent” hereafter), electronic health record (EHR) data will be collected from UC Davis, and daily weekday FCR observations will be performed. To gather necessary data for the intervention evaluation, qualitative interviews will be performed.

- INCLUSION: (NEONATES) Neonates aged <365 days admitted to UC Davis neonatal intensive care unit (NICU) during the study period who have one or more parent or guardian that self-reports their preferred language to be English. This parent must also be non-incarcerated and aged  $\geq 18$  years.
- EXCLUSION: (NEONATES) Age > or = 365 days. Neonates with visitation or information restrictions placed by child protective services. Neonates with more than one admission during the trial period will be included only on their first admission.
- INCLUSION: (QUALITATIVE INTERVIEWS) Parents/guardians of the eligible patients (described above) and NICU clinicians (e.g., nurses, physicians). Age 18 years and older.
- EXCLUSION: (QUALITATIVE INTERVIEWS) Age less than 18 years. Non-English speaking.
- INCLUSION: (SURVEY) Parents/guardians of the eligible patients (described above). Age 18 years and older.

**PROTOCOL TITLE: Virtual Family-Centered Rounds in the Neonatal Intensive Care Unit:  
A Randomized Clinical Trial**

- EXCLUSION: (SURVEY) Age less than 18 years. Non-English speaking.

**5) Study Timelines**

We anticipate this trial will begin ~2/1/2023. We will begin enrolling subjects at trial onset. We will enroll subjects (neonates) and assign to either the intervention or control arm for 12 months. Each subject (neonate) will be included for the duration of their hospitalization.

We will follow this 12-month period with 1 month of rounding observations for data collection. We will also continue to collect surveys at 0, 30, 60, and 90 days from discharge. Therefore, survey data collection will continue until 16 months from the trial onset.

Regarding qualitative interviews for the intervention evaluation (Aim 3), those will continue for 18 months from the trial onset.

The estimated date to complete this study is therefore ~8/1/2024.

**6) Study Endpoints**

Primary study endpoint is completing 12 months of trial enrollment. Secondary study endpoints include (a) completing the 13 months (12 + 1 month after last enrollment) of daily weekday rounding observations of subjects; (b) completing the last survey for the last discharged patient (at 90 days from discharge); (c) completing qualitative data analysis and integration for the mixed methods intervention evaluation.

**7) Procedures Involved**

**OVERVIEW:** The overall objective of this study is to conduct a randomized trial comparing virtual family-centered rounds (FCR) to standard FCR for NICU patients and to conduct an intervention evaluation of the virtual FCR intervention. This study protocol involves the UC Davis NICU (n=447 neonates) and uses a 2:1 intervention-to-control arm ratio. The endpoint of the study includes completing the 12-month enrollment (intervention delivery) period plus the 1 additional month of rounding observation data collection plus the 90-day follow-up parent survey for neonates discharged home during the study period. Thus a 16-month total period (12 months + 1 month + 90 days). The end of the 16-month period will be when neonates will no longer be assigned to standard FCR (control) versus virtual FCR (intervention) and no more neonates will be eligible for the study (which occurs at 12 months) followed by completion of the additional 1-month rounding observation data collection followed by the last survey recruitment invitation (which occurs 90 days following the last eligible patient is discharged home to obtain 90-day outcome measures). Hypotheses include the following: (1) The virtual FCR (intervention) group will have a higher parent FCR attendance proportion compared to the standard FCR (control) group; (2) Virtual FCR neonates will have (a) greater breast milk feeding, (b) reduced growth failure, (c) fewer medical errors, and (d) shortened length of stay compared to standard-of-care neonates; (3) Parents of virtual FCR neonates will report (a) better experience, (b) higher activation, (c) less distress, and (d) better

**PROTOCOL TITLE: Virtual Family-Centered Rounds in the Neonatal Intensive Care Unit:  
A Randomized Clinical Trial**

quality of life compared to parents of standard-of-care neonates. To conduct the intervention evaluation, we will apply the 5 dimensions of the RE-AIM framework (Reach, Effectiveness, Adoption, Implementation, Maintenance) and use a mixed methods approach with a convergent design. Data integration will occur by merging data in the analysis and reporting phases.

**ASSIGNMENT TO CONTROL VERSUS INTERVENTION:** The unit of randomization is at the subject (neonate) level. The study statistician will generate a random allocation list and employ allocation concealment to assign eligible subjects with a 2:1 intervention-to-control arm ratio. During the 12-month enrollment (intervention delivery) period, a research coordinator will open the sequentially numbered assignments to invite parents of neonates assigned to the intervention arm to sign up for virtual FCR. Neonates of parents accepting this offer will be considered “subscribed.” For neonates with more than one eligible parent, separate subscription invitations will be used for each parent.

**DELIVERY OF INTERVENTION:** We will use Extended Care as the software interface for virtual FCR. This secure platform meets HIPAA security rules and launches from the electronic health record. Parents will use the Extended Care application on their personal computer or smart device. The NICU medical team will use Extended Care on a computer on wheels with a speaker and camera. Virtual FCR will be available for parents of subscribed neonates to attend Monday through Friday. For neonates with a subscribed parent, a NICU team member will launch an ExtendedCare telehealth visit (“virtual room”) from the patient’s Epic chart. From ExtendedCare, a NICU team member will use the “invite” feature to invite the subscribed parent(s); the parents then receive a message to their email/cell phone that includes their child’s unique Extended Care link. The parent(s) can use this link, if desired, to enter the “virtual room.” If a parent joins, they will establish the live, bidirectional audio and visual connection. FCR will then proceed in usual fashion. Parents can participate in virtual FCR as much, or as little, as they choose. They can also participate in FCR in person (standard of care) or not participate at all.

**QUALITATIVE INTERVIEWS:** The stakeholder engagement team members will assist with recruitment of the interview participants. Stakeholders or a research team member will recruit eligible interview participants. They will hand-deliver a flyer to the parents/guardians of eligible patients at the time of [i.e., 2 days before the anticipated] hospital discharge. Alternatively, since parents are not often at the bedside for in-person recruitment, they will send a secure message from StudyPages or make a phone call to invite participants to participate in an interview. Non-respondents will be contacted once 7 days later by a research coordinator through StudyPages. Clinician (e.g., nurses, physicians) interview participants will be identified by stakeholder or research team members. Recruitment emails or Secure Chat messages will be sent to the clinicians. Repeat email/message outreach will be made to the clinician non-respondents at 2 and 4 weeks following initial outreach. Participants will receive \$50 for participating in an interview. Interested participants will have one in-depth interview that lasts ~45 minutes. Interviews will be in-person when possible, but otherwise by telephone or videoconference. Interviews will be audio recorded, transcribed, and reviewed for accuracy by the interviewer. Transcriptions will be uploaded into ATLAS.ti.

**DELIVERY OF SURVEY:** Parents will be invited to complete their first survey at

**PROTOCOL TITLE: Virtual Family-Centered Rounds in the Neonatal Intensive Care Unit:  
A Randomized Clinical Trial**

the time of [i.e., 2 days before the anticipated] discharge. If a neonate has two eligible parents, separate invitations will be sent to each parent. Recruitment will occur via giving them a packet at discharge. The packet will contain a recruitment letter (flyer), a scannable barcode (to access the survey electronically if preferred), a website link (another alternative to access the survey electronically if preferred), and a paper version of the survey. Alternatively, since parents are not often at the bedside for in-person recruitment, the research assistant will send a secure message/email from StudyPages or make a phone call to invite participants to participate in an interview. Parents can complete the survey themselves or verbally with the research assistant who will directly input verbal responses into REDCap. The research assistant will make 3 daily attempts of outreach and follow up with non-respondents 7 days later. If a survey is not returned within 21 days of discharge, the survey will be considered a non-response. The survey delivery process from a Secure Chat message/email or phone call will occur at 30, 60, and 90 days to administer the subsequent survey packets (with 3 daily attempts and follow-up 7 days later and a 21-day response time limit). Electronic surveys will be conducted in REDCap. Paper surveys will be kept in a locked box in the locked physician workroom until collected by a research assistant, who will transfer the data into REDCap and then destroy the paper copy. For parents with more than one neonate enrolled in the study (i.e., twins/multiples), the parents will only receive one survey packet per child. The survey will be sent to the parents at the time that one of their children first discharges from the NICU (and each subsequent 30 day period will be based off that first child's discharge date). For subsequent siblings discharged at later dates, a research assistant will use StudyPages to message/call parents to obtain the responses to (a) questions #1 and 2 of the 30-day survey and (b) question #1 of the 90-day survey. These questions relate to the outcomes of (a) 30-day revisit/readmission and (b) 90-day breastmilk feeding. The research assistant will directly input the responses into REDCap.

**DATA COLLECTION:** Data collection will include daily weekday virtual FCR observations; parent surveys; and review of the EHR, incident reports, and helpdesk technical issues log. Outcomes (for Aims 1-3) will include the following: FCR parent attendance proportion (captured using weekday rounding observations), length of stay (captured using EHR data), breast milk feeding initiation and breast milk feeding at discharge (captured using EHR data) and at 90 days after discharge (captures via parent via parent/guardian survey), growth failure and growth velocity (captured using EHR data), time to first social work contact (captured using EHR data), temperature instability (captured from an existy NICU quality dataset), feeding difficulty (captured from an existy NICU quality dataset), central line-associated bloodstream infection (captured from an existy NICU quality dataset), central line days (captured from an existy NICU quality dataset), antibiotics days (captured from an existy NICU quality dataset), medical errors (captured using data from EHR, incident reporting system, and solicited reports), 30-day revisit and readmission (captured via EHR and survey) parent experience and family-centered care (captured via parent/guardian survey at discharge), parent activation (captured via parent/guardian survey at discharge), parent distress: depression and anxiety (captured via parent/guardian survey at 0, 30, 60, 90 days from discharge), parent sleep (captured via parent/guardian survey at 0, 30, 60, 90 days from discharge), and parent quality of life (captured via parent/guardian survey at 0, 30, 60, 90 days from discharge).

RE-AIM (Aim 3) implementation evaluation data collection will include the

**PROTOCOL TITLE: Virtual Family-Centered Rounds in the Neonatal Intensive Care Unit:  
A Randomized Clinical Trial**

following: subscribed vs. not subscribed parents among intervention-arm parents, heterogeneity of intervention effects (interactions between neonate/parent characteristics and the intervention effect), virtual FCR attempts with technical issues (sounds, video, other), trial-related 24/7 helpdesk line calls, ExtendedCare wait time when parent(s) join, ExtendedCare connection time, device model (e.g., iPhone, Android, etc.) that parent uses to connect to the ExtendedCare visit, interruptions requiring a break in rounds due to a delivery or new admission, and virtual FCR use with NICU parents post-trial (maintenance).

Data will be collected from both the intervention and control arm subjects. The EHR access for data collection will only occur in a retrospective fashion. The interaction with the control arm group parents will therefore include an invitation via letter (flyer) to participate in the surveys. The observations of FCR will be conducted by either a research team member or a NICU team member who already participates in FCR as part of clinical care. The information being recorded from the observations is whether or not parent(s) are present at FCR, and if so, what type of attendance (in person vs. virtual).

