This study is evaluating a systems-level intervention; a system-level intervention means that we are doing an intervention on how we deliver healthcare. In other words, our intervention is a test of change to the healthcare system. In this case, the system is how we deliver family-centered rounds. The study team will not be able to determine the feasibility and implementation of the pilot project without collecting the implementation data on all patients. It is important that we collect data on all eligible subjects, because we want to ensure that we include gathering data from underserved populations in order to learn how to better provide them with clinical services that meet/address their unique needs. This aspect is particularly relevant for telehealth interventions, whereby the ditigal divide is potentially designing/deliverying telehealth services that do not serve diverse populations. It is therefore important to have all of our diverse groups represented in our data in order to conduct our comprehensive intervention evaluation (Aim 3). We recognize the limitation that our survey-based outcomes (for Aims 1 and 2) will only gather data from those who complete the survey, and thus the conclusions from survey-based data will only be generalizable to similar populations as those represented in those surveys. However, our other outcomes (that rely on FCR observations and review of the EHR, incident reports, and

**PROTOCOL TITLE: Virtual Family-Centered Rounds in the Neonatal Intensive Care Unit:  
A Randomized Clinical Trial**

helpdesk technical issues log) will include all our subjects – and thus represent diverse groups.

Since this is a systems-level intervention, only collecting data on consented patients will provide Aim 3 (intervention evaluation) results that are biased and therefore not useful. We cannot understand how to refine and deliver our telehealth intervention (and thus improve this clinical service line) without having data on all eligible patients. Although we will need to collect data on every patient, the family members in the intervention group can choose if and how much to use the intervention (they can decide to never provide their cell phone number and to never use telehealth for FCR).

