## 18) Provisions to Protect the Privacy Interests of Subjects

All information will be kept in secure REDCap or Excel databases and the only link between the patient and the REDCap will be a Study ID. We will use a "Participant Log" excel file to store data that links the Study ID with the subject. This log will include the following information: Study ID, patient name, MRN, CSN, intervention vs. control arm, admit date, enrolled date, parent identify (e.g., "mom"), parent cell/email preferred contact, subscription status, and disposition. This "Participant Log" will be stored on the secure UC Davis server.

Families will be free to use the intervention if/when it works for them. Families randomized to the intervention can opt out of using it entirely, with no penalty to them or their child. Families are free to answer (or not answer) the surveys the week of discharge and at 30, 60, and 90 days after discharge, with no penalty to them or their child.

Only members of the research team will have access to the data.

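### Survey answers may be taken verbally by staff who are not masked to arm, and completion mode is not recorded, so interviewer and mode effects on the Hypothesis 1b outcomes could not be separated from a true effect

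*Combined protocol and SAP*

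**What the plan says.** Protocol section 7 (survey delivery) offers paper, electronic and spoken completion: "Parents can complete the survey themselves or verbally with the research assistant who will directly input verbal responses into REDCap". The same paragraph has the research assistant message or call parents of later-discharged siblings to obtain the 30-day revisit and 90-day breast milk answers, and enter them.

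Section 18 describes one Participant Log. Its fields include "Study ID, patient name, MRN, CSN, intervention vs. control arm, admit date, enrolled date" and also "parent cell/email preferred contact, subscription status, and disposition". The access rule is: "Only members of the research team will have access to the data".

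On outreach, section 7 sets one procedure without naming an arm: "The research assistant will make 3 daily attempts of outreach and follow up with non-respondents 7 days later". Of the material handed over at discharge it says: "The packet will contain a recruitment letter (flyer), a scannable barcode". Later in section 7, under data collection, comes this sentence: "The interaction with the control arm group parents will therefore include an invitation via letter (flyer) to participate in the surveys".

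Section 7 gives the opening of assignments and the subscription invitations to a research coordinator, and the surveys to a research assistant. It does not say that these must be different people.

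The SAP analyses complete cases under missing at random, with multiple imputation as a sensitivity analysis. Neither document describes masking of survey staff, an interview script, or the recording or analysis of completion mode.

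**The concern.** Parents cannot be blinded to whether they were offered virtual rounds, and all four parts of Hypothesis 1b are self-reports. In that setting the safeguards left to the trial are to keep the arm from whoever takes the answers and to know which answers were spoken. The plan specifies neither.

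An assistant who knows the arm can, without meaning to, prompt, clarify or code answers differently. Spoken answers may also differ from private ones. If either effect differs between arms, it enters the estimated intervention effect. If mode was never recorded, the question cannot be examined afterwards.

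The exposed outcomes are the survey outcomes: experience, activation, distress, sleep, quality of life, and the survey-based parts of 30-day revisit and 90-day breast milk feeding. The last two are more factual and so probably less sensitive. The primary outcome comes from weekday rounding observations and lies outside this point, as do outcomes taken from the health record.

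**Working it through.** **1. The plan's own figures (section 8, sample size).** Inputs: 25% reduction in geometric mean length of stay, log-scale SD 1.0, 2:1 allocation, two-sided 5%, 80% power, 4% attrition, 75% survey response.

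- Effect on the log scale: |ln 0.75| = 0.288.
- Required: 143 control and 286 intervention, total 429. Inflated: 429 / 0.96 = 447, as stated.
- Power at 286 and 143: SE = sqrt(1/286 + 1/143) = 0.102; 0.288 / 0.102 = 2.81; Φ(2.81 − 1.96) = 80.2%.
- Survey sample: 0.75 × 429 = 321.75, stated as 321.

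All of these reproduce. The plan states no figure for interviewer or mode effects, so there is none to correct.

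**2. Precision of a survey comparison.** Splitting 321 respondents 2:1 gives 214 and 107 (assuming equal response by arm, independent respondents and a continuous outcome in SD units).

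- SE = sqrt(1/214 + 1/107) = 0.118 SD.
- Difference detectable with 80% power: (1.96 + 0.84) × 0.118 = 0.33 SD.

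**3. What a small reporting shift would do.** Suppose there is no true effect and a net shift *b* toward virtual rounds. The chance of a significant result favouring virtual rounds is 1 − Φ(1.96 − b/SE). The values of *b* are assumptions.

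| Assumed shift b (SD) | b/SE | Chance of a significant favourable result |
|---|---|---|
| 0 | 0 | 2.5% |
| 0.05 | 0.42 | 6% |
| 0.10 | 0.84 | 13% |
| 0.15 | 1.27 | 24% |
| 0.20 | 1.69 | 39% |

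A shift of 0.10 SD arises, for example, if half of the intervention-arm answers are spoken and those are moved by 0.2 SD, with no such movement in controls: 0.5 × 0.2 = 0.10. The documents give neither the spoken share nor the size of any movement.

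**4. Can survey staff know the arm?** Section 7 has the assistant message and call parents, which requires contact details. The only place where the documents list such details is the Participant Log, which also carries arm and subscription status. No rule withholds those fields from survey staff. Section 7 also lets research team members observe rounds and record virtual versus in-person attendance, which is a second route to knowing the arm. The documents permit knowledge of the arm; they do not say that it occurs.

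**The case against.** The strongest reply has four parts.

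- **Roles and tools are already distinct.** A coordinator opens assignments and an assistant runs surveys, using StudyPages, which section 8 names as the tool for communicating with participants. The assistant may never open the log. This stands to the extent that use of the log is an inference. But the documents do not say what StudyPages displays, nor that the roles must be kept apart.
- **Self-completion is available.** Paper, a barcode and a web link are all offered, so the spoken share may be small. That is possible, but without a mode field no one will know.
- **The SAP already adjusts.** It lists parent covariates, including education and digital literacy, and plans multiple imputation; section 8 acknowledges that survey results represent respondents only. These measures bear on non-response and imbalance. None can correct an answer that was recorded under an interviewer's influence.
- **Masking gains little when parents know their arm.** This largely stands. Masking the assistant removes the interviewer's part and leaves parents' own reporting bias.

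A reader might go further and infer that survey outreach differs by arm, because section 7 mentions a flyer for control parents. The documents do not support this. The sentence says what control contact will include, not what it is limited to; the same flyer is in the general packet; and the outreach steps name no arm. Nor does section 8's remark on intervention families, that "they can decide to never provide their cell phone number and to never use telehealth for FCR", help that reading: it concerns declining telehealth, and the log's contact field is not confined to one arm.

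**Conclusion.** The point holds as a cheap improvement to the survey outcomes. It does not threaten the primary analysis. The plan allows unmasked verbal collection of subjective outcomes and records nothing that would let its influence be examined.

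The illustrative size is a 13% chance of a falsely favourable result, against 2.5%, for an assumed 0.10 SD shift; that shift is 0.10 / 0.33, or about 30%, of the detectable difference. The figure rests on the assumed shift, on 214 and 107 independent respondents, and on no true effect. It shows sensitivity and does not predict the bias in this trial.

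A reader might also infer that unequal response between arms would push results toward virtual rounds. The documents give one overall response rate and no basis for a direction. If responders exceed non-responders by *d* in both arms, the bias is d × (control response − intervention response). Higher intervention response would then work against virtual rounds when responders fare better, and in its favour when they fare worse. No size or sign is claimed here for differential response.

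**What to change.** 1. Give survey staff a contact list, a StudyPages view and a REDCap survey project that omit arm and subscription status. State that the coordinator who opens assignments and handles subscriptions does not administer surveys.
2. Record the mode of each survey (paper, electronic, verbal). Report response and mode by arm. Add to the SAP a repeat of the Hypothesis 1b analyses on self-completed surveys. Because parents choose their mode after randomization, this should be a sensitivity analysis beside the main one, not a replacement.
3. As a clarification only, add to the control-arm sentence in section 7 (data collection) that the survey outreach set out earlier in that section applies identically to both arms.

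The cost is a split log, one REDCap field, some division of duties among existing staff and a few sentences. Sample size and intervention do not change. The limits are that some parents will reveal their arm in conversation, so masking is partial, and that parents' own reporting bias remains.
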